2. BACKGROUND AND RATIONALE

2.1 Introduction

Aerogen Pharma is developing VentaProst, an inhaled epoprostenol, as an integrated medication/device combination product consisting of a FDA-approved and commercially available epoprostenol sodium intravenous (IV) solution (Flolan®) administered by a precision single-patient use custom nebulizer compatible with ventilator support equipment used in operating rooms (ORs) and intensive care units (ICUs). VentaProst is being investigated as a perioperative pulmonary vasodilator for patients undergoing cardiac surgery with cardiopulmonary bypass (CPB). VentaProst therapy will be transferable from anesthesia ventilator to patient transport to ICU ventilator and on to nasal cannula post-extubation, thus maintaining vasodilation and preventing rebound pulmonary hypertension (PH) during patient transition from surgery.

Flolan (epoprostenol sodium), also known as prostacyclin, PGI₂ or PGX, a metabolite of arachidonic acid, is a naturally occurring prostaglandin. Epoprostenol has two major pharmacological actions: (1) direct vasodilation of pulmonary and systemic arterial vascular beds, and (2) inhibition of platelet aggregation. In animals, the vasodilatory effects of epoprostenol reduce right and left ventricular afterload and increase cardiac output (CO) and stroke volume.

Epoprostenol is rapidly hydrolyzed at neutral blood pH and is also subject to enzymatic degradation. No available chemical assay is sufficiently sensitive and specific to assess the *in vivo* human pharmacokinetics (PK) of epoprostenol. Animal studies using tritium-labelled epoprostenol have indicated a high clearance (93 mL/min/kg), small volume of distribution (357 mL/kg), and a short half-life (2.7 minutes). During infusions in animals, steady-state plasma concentrations of tritium-labelled epoprostenol were reached within 15 minutes and were proportional to infusion rates.

Epoprostenol is metabolized to 6-keto-PGF1 α (formed by spontaneous degradation) and 6,15-diketo-13,14-dihydro-PGF1 α (enzymatically formed), both of which have pharmacological activity at orders of magnitude less than epoprostenol in animal test systems. 6-keto-PGF1 α has been used as a surrogate PK metabolite for epoprostenol, but does not accurately represent the local active concentration of epoprostenol in the lungs with an elimination half-life of approximately 20-30 minutes. Additionally, large and rapid fluctuations in endogenous epoprostenol as indicated by 6-keto-PGF1 α levels perioperatively in cardiac surgery confound the exogenous epoprostenol contribution for PK determinations (Ylikorkala 1981).

Inhalation delivery of epoprostenol in cardiothoracic surgery patients offers an attractive alternative to IV delivery because it minimizes systemic exposure associated with clinically hazardous effects such as hypotension and exacerbation of pulmonary and cardiac shunts. The rationale for administering epoprostenol continuously as an aerosol through ventilator support equipment stems from its extremely short half-life of approximately three minutes *in vivo*. This enables delivery of high local concentrations of vasodilator into the lung vasculature, reducing PVR (pulmonary vascular resistance)

and RH (right heart) afterload. As a result, the use and effectiveness of inhaled epoprostenol is widely reported [Buckley and Feldman, 2010; De Wet, 2004; Fattouch, 2005; Fattouch, 2006; Hache, 2003; Haraldsson, 2001; Khan, 2009; Ocal, 2005] in a variety of applications including mitral valve surgery. Nonetheless, such practices remain off-label, as inhaled epoprostenol is not FDA-approved for this indication or route of administration.

Clinical centers have independently developed protocols to deliver the IV formulation as aerosol by mechanical ventilation and nasal cannula using commercially available nebulizers. The nominally prescribed dose of 50 ng/kg/min is administered without regard for system efficiencies with these protocols. This results in dose delivery to the lungs that is assumed to be within the flat portion of the hemodynamic dose response curve to inhaled epoprostenol.

A review of published literature demonstrates that the use of inhaled epoprostenol in patients undergoing cardiothoracic surgery is safe and well tolerated. Doses of 10 – 100 ng/kg/min administered through a wide variety of conventional aerosol delivery methods led to improved hemodynamics (such as lowering of pulmonary arterial pressure [PAP] and pulmonary vascular resistance [PVR]), improved cardiac index (CI) and right ventricular ejection fraction (RVEF), easier separation from CPB, reduced intubation times, and shorter stays in the ICU.

The VentaProst nebulizer delivery platform is designed to accurately and precisely administer aerosol to the lungs of critically ill patients requiring support via mechanical ventilation and/or supplemental oxygen by nasal cannula. The intent is to standardize the critical components for consistent and quantifiable aerosolized epoprostenol delivery by mechanical ventilator and nasal cannula systems. Aerogen Pharma has evaluated various delivery systems used for conventional aerosol administration of epoprostenol to the lungs (in accordance with each site's standard of care practice guideline) and has estimated the equivalent dose by VentaProst.

The intent of Part I of the Phase 2a study is to demonstrate that the estimated VentaProst dose has the same hemodynamic effect as aerosolized Veletri at 50 ng/kg/min (in accordance with each site's standard of care guidelines). The assumption is that the hemodynamic response from the aerosolized Veletri dose will not change significantly with minor changes in dose (flat portion of the dose response curve). When patients are converted to VentaProst, a determination is made whether or not the hemodynamic response is similar by being at least as much as the response with the aerosolized epoprostenol dose. If the hemodynamic response with VentaProst is less than that of the aerosolized Veletri dose, the dose will be increased until a similar response is observed. VentaProst dosing will not be titrated downward to match the aerosolized Veletri hemodynamic response because of the possibility that the patients' requirements for pulmonary vasodilation may have improved since the start of aerosolized Veletri.

Part II of the study is intended to start VentaProst dosing at a dose that will show an improved hemodynamic response by increasing the dose (steep portion of the dose response curve). The intent is to demonstrate that simple dose adjustments to the VentaProst delivery device flow of epoprostenol to the nebulizer can rapidly optimize

VentaProst dose administration.

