3. STUDY OBJECTIVES

3.1 Primary Objective

The primary objective of this study is to identify the relative dose equivalency between effective conventionally administered aerosolized Veletri and VentaProst doses.

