4. OVERALL STUDY DESIGN AND PLAN

4.1 Part I

The first part of this study will be conducted in approximately 10 consented post-operative cardiothoracic surgery patients on CPB who are receiving aerosolized Veletri (in accordance with each site's standard of care guidelines) and who demonstrate at least a 15% improvement in one or more hemodynamic parameters (as defined by the clinical team) when treated with aerosolized Veletri. This part of the study is designed to demonstrate the dose equivalence between aerosolized Veletri and VentaProst using a patient's hemodynamic parameters, with the goal to determine the VentaProst dose necessary to achieve a hemodynamic response that is not less than 90% of the effect observed with 50 ng/kg/min aerosolized Veletri. Arterial oxygen saturation (SaO₂) must be maintained at or above the level obtained with aerosolized epoprostenol administration.

Qualifying patients will:

- Receive aerosolized Veletri 50 ng/kg/min in the OR/ICU
- Have hemodynamic parameters measured before and after aerosolized Veletri administration to determine changes

- *IF AT LEAST A 15% IMPROVEMENT IN ONE OR MORE HEMODYNAMIC PARAMETERS (AS DEFINED BY THE CLINICAL TEAM) IS SEEN WITH AEROSOLIZED VELETRI AFTER STABILIZATION IN THE ICU:*
 - Be administered VentaProst as follows: Setup VentaProst inline to the ventilator circuit, start nebulization, then stop conventional Veletri pump flow and nebulizer while still inline. Do not remove Veletri administration system until VentaProst administration is confirmed
- *IF LESS THAN A 15% IMPROVEMENT IN ONE OR MORE HEMODYNAMIC PARAMETERS (AS DEFINED BY THE CLINICAL TEAM) IS SEEN WITH AEROSOLIZED VELETRI AFTER STABILIZATION IN THE ICU:*
 - Not be administered VentaProst
- Receive a calculated equivalent starting dose of 17 ng/kg/min of VentaProst while still on mechanical ventilation
- Receive increases in the VentaProst dose in 20% increments (refer to the VentaProst Pharmacy Manual) every 15 minutes until at least 90% of the hemodynamic effect observed with 50 ng/kg/min aerosolized Veletri is achieved

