Once a VentaProst dose equivalence has been achieved, patients will be weaned from VentaProst. VentaProst weaning will occur from mechanical ventilation only. If the patient has been extubated and is on institution's standard of care delivery system for administering aerosolized Veletri, weaning will occur in accordance with each site's standard of care guidelines for weaning of aerosolized Veletri. The table below shows the typical weaning steps for aerosolized Veletri from mechanical ventilation. If weaning from VentaProst occurs while on mechanical ventilation, doses will be decreased in 20% increments of the VentaProst equivalent dose.

Weaning Guideline

Aerosolized Veletri (from Ventilator)	VentaProst (from Ventilator)
50 ng/kg/min	Dose Equivalence to aerosolized Veletri 50 ng/kg/min
40 ng/kg/min	80% of Dose Equivalence
30 ng/kg/min	60% of Dose Equivalence
20 ng/kg/min	40% of Dose Equivalence
10 ng/kg/min	20% of Dose Equivalence

Patients on mechanical ventilation will be weaned from VentaProst slowly due to concern that VentaProst is providing significant clinical benefit and to avoid a rebound effect. Doses will be decreased in increments of 20% of the VentaProst equivalent dose, with a minimum of 30 minutes between changes, down to 20% of the dose before discontinuation. The VentaProst weaning process should occur in isolation to other

treatment changes (no changes in inotropes, pressors or vasodilators). Patients will be observed closely before, during, and after dosing changes. In the event patients demonstrate signs of hemodynamic instability (changes in combined hemodynamic parameters) or a decrease in oxygenation indicated by either arterial or central blood oxygenation saturation during downward titration, the VentaProst dose will be returned to its previous level. Once patients have been stable for at least 15 minutes, repeat attempts at dose reduction may be undertaken. The process will continue until patients are fully weaned from VentaProst. A final PD measurement will be collected 15 to 30 minutes after discontinuation of VentaProst.

Patients will be monitored for safety and PD efficacy throughout the aerosolized Veletri and VentaProst administrations.

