7. PHARMACODYNAMIC ASSESSMENTS

7.1 Primary Endpoint

Determination of the equivalent dose of VentaProst necessary to achieve a hemodynamic response that is not less than 90% of the effect observed with 50 ng/kg/min aerosolized Veletri.

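### Part I can show that a VentaProst dose is sufficient to hold the Veletri effect, but matching against one Veletri dose assumed to be on the plateau cannot identify relative dose equivalency

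*Combined protocol and SAP*

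**What the plan says.** The primary objective (synopsis and section 3.1) is to "identify the relative dose equivalency between effective conventionally administered aerosolized Veletri and VentaProst doses". The primary endpoint in section 7.1 is "Determination of the equivalent dose of VentaProst necessary to achieve a hemodynamic response that is not less than 90% of the effect observed" with Veletri 50 ng/kg/min; section 12.5.1 repeats it and leaves the detail to the statistical analysis plan.

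Section 2.1 makes two statements about the reference dose. Of current practice it says: "The nominally prescribed dose of 50 ng/kg/min is administered without regard for system efficiencies with these protocols", and it gives the outcome as "dose delivery to the lungs that is assumed to be within the flat portion of the hemodynamic dose response curve". For Part I it adds the assumption that the Veletri response "will not change significantly with minor changes in dose (flat portion of the dose response curve".

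The VentaProst side is set out in section 4.1: "Receive a calculated equivalent starting dose of 17 ng/kg/min of VentaProst while still on mechanical ventilation", then increases of 20% every 15 minutes until the 90% criterion is met. Section 2.1 rules out downward titration to match the response and explains that the patient's need for vasodilation may have improved in the meantime. On the origin of the starting dose it says only that the sponsor "has estimated the equivalent dose by VentaProst" after evaluating delivery systems.

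**The concern.** Effect can be converted into relative dose only where effect changes with dose. Part I observes Veletri at one dose, which the protocol itself places where effect changes little. VentaProst is credited with the first tested dose to reach 90% of that effect, with no upper limit on the response. A result such as 17 matching 50 may therefore reflect the shape of the curve, the 90% tolerance, a real difference in delivery, or a mixture, and Part I has no data to separate them.

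Nothing else in the documents supplies the missing information. Part II studies VentaProst alone, in different patients. Section 9 states that pharmacokinetic assessments do not apply. Section 12.5.1 contains no dose-response or relative-potency model. Lower VentaProst doses would not cure the problem, because Veletri would still be observed at one dose on the assumed plateau. At stake is the primary objective: a matched dose reported as an equivalence could be carried into later work as if it were a potency ratio.

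**Working it through.** **Inputs from the protocol.** Veletri 50 ng/kg/min; VentaProst start 17 ng/kg/min; upward steps of 20%; stop at the first dose with at least 90% of the Veletri effect (sections 2.1, 4.1, 7.1).

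**The plan's own figure.** 17/50 = 0.34, an implied ratio of 50/17 = 2.94. The 17 cannot be re-derived, because no delivery efficiencies are given. One link does check: 20% of 17 is 3.4, the Part II start and step.

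**Assumptions, not in the documents.** An Emax curve, E(D) = D/(D + ED50), with no measurement error. Steps are additive at 3.4 ng/kg/min, since section 4.1 does not say whether the 20% compounds. The test product is identical to Veletri, so the true ratio is 1.0.

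**Dose giving 90% of the effect of 50.** Let f = 50/(50 + ED50) be the share of maximum effect reached at 50, and x = 50/ED50 = f/(1 − f). Solving E(D) = 0.9 × E(50) gives D90 = 45/(1 + 0.1x). The recorded dose is the first of 17, 20.4, 23.8, 27.2, 30.6, 34.0, 37.4, 40.8, 44.2, ... at or above D90.

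| f | x | D90 (ng/kg/min) | Recorded dose | Apparent ratio (50/recorded) |
|---|---|---|---|---|
| 0.50 | 1 | 45/1.1 = 40.9 | 44.2 | 1.13 |
| 0.80 | 4 | 45/1.4 = 32.1 | 34.0 | 1.47 |
| 0.90 | 9 | 45/1.9 = 23.7 | 23.8 | 2.10 |
| at least 0.943 | at least 16.5 | at most 17.0 | 17 | 2.94 |

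The last row is a cap: nothing below 17 is tested for matching, so no larger ratio can be recorded. With compounding steps (17, 20.4, 24.5, 29.4, 35.3, 42.3) the recorded doses are 42.3, 35.3, 24.5 and 17, and the ratios 1.18, 1.42, 2.04 and 2.94.

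**When an identical product stops at 17.** It needs 17(50 + ED50) ≥ 45(17 + ED50), that is 850 − 765 ≥ 28 × ED50, so ED50 ≤ 85/28 = 3.04 and f ≥ 50/53.04 = 0.943. With Hill slopes of 1.5, 2 and 3 the limits are ED50 ≤ 4.64, 6.07 and 8.30, where 50 ng/kg/min gives 97.3%, 98.5% and 99.5% of maximum.

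**How much is the 90% tolerance.** On a straight line with no plateau, 90% of the effect is reached at 45, a ratio of 50/45 = 1.11 before the steps are applied. Anything beyond that in D90 is curvature.

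**What a stop at 17 tells us.** If VentaProst has potency r relative to Veletri, stopping at 17 requires 17r ≥ D90. With Hill 1 this means r ≥ 0.44 (ED50 1), 0.99 (ED50 3), 1.32 (ED50 5) or 1.76 (ED50 10). It is a one-sided bound that moves with an unknown curve.

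**The case against.** The strongest reply is that the protocol claims flatness only for minor changes in dose, and 50 to 17 is a 66% reduction. This stands as a limit on the size of the problem. A reader might infer that any product identical to Veletri would match at 17; the documents do not support that. In the table, an identical product stops above 17 when f is 0.50 to 0.90, and Part I would then have some power to discriminate. The recorded dose would still be below the true equivalent of 50, by an amount that cannot be corrected without knowing the plateau width.

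Second, the calculation uses only the 90% criterion. Section 4.1 also requires arterial saturation at or above the Veletri level, section 2.1 speaks of a response at least as large, and Table 1 footnote 9 asks for matching measurements. Stricter readings would move the recorded dose upward. They would not supply a Veletri dose-response.

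Third, section 2.1 gives the intent as showing that the estimated dose has the same effect as Veletri 50 ng/kg/min, which the design can address, and no passage promises a delivery-efficiency conclusion. That is fair. Comparison with the nominal dose used in practice is a defensible choice in a descriptive Phase 2a study of about 10 patients per part. The difficulty is that section 3.1 names something more than equal effect.

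Finally, the weaning guideline lists steps such as "80% of Dose Equivalence" beside 40 ng/kg/min of Veletri, and a reader might take this as a claim of proportional equivalence. It need not be: each column steps down from that product's own full dose, and no equal effect along a row is asserted.

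**Conclusion.** The concern holds as a mismatch between objective and design. Part I can establish a sufficient VentaProst dose; it cannot identify the relative dose equivalency in section 3.1. Under the stated Emax assumptions the apparent ratio for an identical product runs from 1.13 to the cap of 2.94, depending on how far up the curve 50 ng/kg/min lies. These figures illustrate the possible distortion and are not an estimate of it: ED50, the Hill slope and the form of the steps are assumptions, and part of each shift is the 90% tolerance itself.

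The qualitative conclusion does not depend on the particular curve. It needs only one reference dose, a curve of unknown slope around it, and a one-sided matching rule. This should be fixed, but it concerns what may be concluded and does not invalidate the data collection.

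**What to change.** In the synopsis and sections 3.1, 7.1 and 12.5.1, restate the Part I objective and endpoint as the lowest VentaProst dose tested that gave at least 90% of the effect of Veletri 50 ng/kg/min, and call it a sufficient dose. In 12.5.1, report patients who meet the criterion at the first dose as at most 17 ng/kg/min (left-censored), with their number shown separately. Add a sentence that no Veletri-to-VentaProst dose ratio and no conclusion on delivery efficiency will be drawn from Part I effect matching alone.

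Testing flatness from the scheduled weaning readings is not recommended as a decision rule. Weaning begins once the patient is judged stable, so recovery is mixed with dose; extubated patients leave VentaProst and contribute no further readings; and in about 10 patients a slope not distinguishable from zero may only reflect low power. It would also say nothing about the Veletri curve.

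The cost is wording and one reporting convention, plus a weaker headline claim. No change to dosing or data collection is proposed.

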5.4.1 Criteria for Patient Conversion to Conventional Therapy

At any time during VentaProst administration, patients will be crossed-over to standard of care therapy with aerosolized Veletri if they meet one or more of the following pre-defined criteria for a deterioration in their condition:

- Severe postoperative mediastinal bleeding (> 500 mL/hr)

- Hemoptysis
- If a clinically inadequate response to VentaProst is observed, the patient may be converted back to aerosolized Veletri administered in accordance with each site's standard of care guidelines at the investigator's discretion

Additionally, patients will be crossed-over to standard of care therapy with aerosolized Veletri after extubation.

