10.1.4 VentaProst Treatment (ICU)

10.1.4.1 Dosing

Patients who demonstrate at least a 15% improvement in one or more hemodynamic parameters with aerosolized Veletri will be eligible to receive VentaProst. Patients will undergo the following study-related procedures and evaluations:

- Patients will be switched from aerosolized Veletri to receive a calculated equivalent starting dose of 17 ng/kg/min VentaProst while still on mechanical ventilation
- Patients will receive increases in the VentaProst dose in 20% increments (refer to VentaProst Pharmacy Manual) every 15 minutes until at least 90% of the hemodynamic effect observed with 50 ng/kg/min aerosolized Veletri is achieved. Once this has been achieved, the patient will remain on a stable dose of VentaProst for at least 15 minutes
- Measure hemodynamic, oxygenation, and ventilator parameters before and after each VentaProst dose
- Record all concomitant medications
- Record AEs

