12.3 Analyses Sets

All patients who are enrolled in the study and who receive at least one dose of VentaProst will be included in the intent-to-treat (ITT) analyses of pharmacodynamic and safety data. All available data will be used and missing data will not be estimated or carried forward in any statistical summary or analyses.

Descriptive summary statistics include the number of patients, mean, median, percent coefficient of variation (% CV) (if required), standard deviation, and minimum and maximum values (quantitative variables) or the number of patients and percentages by category (qualitative variables). Changes will be assessed as the difference between baseline measurements and the appropriate post-dose measurements unless otherwise specified. Individual patient listings of data will also be provided to allow for review of all pharmacodynamic, safety, and tolerability parameters.

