12.5 Pharmacodynamic Analyses

12.5.1 Primary Endpoint

The primary efficacy endpoint of this study is to determine the equivalent dose of VentaProst necessary to achieve a hemodynamic parameter measurement that is not less than 90% of the effect observed with 50 ng/kg/min aerosolized Veletri.

Further details will be included in the Statistical Analysis Plan.

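### Part I titrates only upward from 17 ng/kg/min, so the recorded equivalent dose is left-censored at 17, and the protocol has no rule for reporting a match at the first dose

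*Combined protocol and SAP*

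**What the plan says.** Section 4.1 has each Part I patient "Receive a calculated equivalent starting dose of 17 ng/kg/min of VentaProst while still on mechanical ventilation". Section 10.1.4.1 raises the dose in 20% increments every 15 minutes "until at least 90% of the hemodynamic effect observed with 50 ng/kg/min aerosolized Veletri is achieved". Section 2.1 rules out the other direction: "VentaProst dosing will not be titrated downward to match the aerosolized Veletri hemodynamic response because of the possibility" that the need for pulmonary vasodilation has improved since Veletri was started.

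The primary objective (3.1) is "to identify the relative dose equivalency between effective conventionally administered aerosolized Veletri and VentaProst doses". The primary endpoint (7.1) is "Determination of the equivalent dose of VentaProst necessary to achieve a hemodynamic response that is not less than 90% of the effect observed" with Veletri 50 ng/kg/min, and 12.5.1 repeats it in nearly the same terms.

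On analysis, section 12.3 gives a general list for quantitative variables: "Descriptive summary statistics include the number of patients, mean, median, percent coefficient of variation", SD, minimum and maximum, plus individual listings. It adds that missing data are not estimated. For the primary endpoint, 12.5.1 says only "Further details will be included in the Statistical Analysis Plan".

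Some patients may never reach a match. Under 5.4.1, "If a clinically inadequate response to VentaProst is observed, the patient may be converted back to aerosolized Veletri" at the investigator's discretion, and extubated patients are crossed over to Veletri. No section says what equivalent dose, if any, these patients are given.

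**The concern.** The endpoint asks for the dose that is necessary, but the design cannot observe a necessary dose below 17. Whether a patient needed 6, 12 or 16.9 ng/kg/min, the record reads 17. This is left-censoring, and ordinary summaries treat the censored value as exact.

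The protocol's own reasoning makes first-dose matches plausible. Section 2.1 assumes that Veletri 50 ng/kg/min lies on the flat part of the dose-response curve, the matching rule is one-sided, and the reason given for not titrating down is that need may have fallen.

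At stake is the primary result. An upper bound could be carried forward as the VentaProst dose equivalent to Veletri 50 ng/kg/min, for a product with no earlier clinical trials (2.2.2).

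**Working it through.** The plan has no computed figure to reproduce: section 12.2 justifies the sample size in words only.

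**Inputs from the protocol.** Start 17 (4.1, 10.1.4.1); comparator 50; upward steps of 20%; stop at 90% of the Veletri effect or more; about 10 patients (section 5). A step of 20% of 17 is 0.2 × 17 = 3.4, giving 17, 20.4, 23.8 and so on. If the steps compound, the doses are 17, 20.4, 24.48 and so on.

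**Floor.** The lowest recordable dose is 17, so the lowest reportable ratio is 17/50 = 0.34.

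**Bounds with no assumed distribution.** These need only that each patient's need is stable during titration. A match at 17 places the need in (0, 17]; a match at 20.4 places it in (17, 20.4].
- 10 of 10 match at 17: recorded mean 17; the data support a mean in (0, 17].
- 7 match at 17 and 3 at 20.4: recorded mean (7 × 17 + 3 × 20.4)/10 = 18.02; lower bound (3 × 17)/10 = 5.10; so (5.10, 18.02].
- 3 match at 17 and 7 at 20.4: recorded mean 19.38; lower bound (7 × 17)/10 = 11.90; so (11.90, 19.38].
- None match at 17: no left-censoring, only step width.

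**Size under assumed distributions.** Assumptions, not from the documents: need T is lognormal with median m and CV 40%, so σ = √ln(1 + 0.4²) = 0.385 and the true mean is m × exp(σ²/2) = 1.077m. Recorded dose = 17 if T ≤ 17, otherwise 17 + 3.4 × ceil((T − 17)/3.4). Share matching at 17 = Φ(ln(17/m)/σ). With n = 10 the median is exactly 17 when at least 6 patients match there. The floor part of the excess is E[max(T, 17)] − E[T]; the rest is step rounding.

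| True median | Share at 17 | True mean | Recorded mean | Excess: floor + rounding | Median exactly 17 |
|---|---|---|---|---|---|
| 10 | 92% | 10.8 | 17.5 | 6.5 + 0.2 | >99% of trials |
| 12 | 82% | 12.9 | 18.1 | 4.9 + 0.3 | 98% |
| 14 | 69% | 15.1 | 19.2 | 3.5 + 0.6 | 84% |
| 17 | 50% | 18.3 | 21.3 | 2.1 + 0.9 | 38% |

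At true medians of 22 and 25 only 25% and 16% of patients match at 17, so the floor matters much less. Compounding steps change little: the recorded mean is 17.5, 18.2 and 19.3 at true medians of 10, 12 and 14.

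**The case against.** A reader might infer that the protocol will report 17 as the equivalent dose. The text does not support that. The mean is 17 only if every patient matches there, and the median only if most do. The list in 12.3 is general and not tied to this endpoint, and 12.5.1 defers detail to the SAP, which 12.1 says will be final before database lock. That SAP could close the gap. What stands is that the protocol, followed as written, has no rule for a first-dose match and names only summaries that would treat it as exact.

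A reader might also infer that Part I fails its purpose. It does not. Section 2.1 says the intent is to show that the estimated dose has the same effect as Veletri, and a finding that 17 is sufficient largely answers that. Ruling out downward titration is a deliberate choice with a stated clinical reason. The mismatch is with the necessary dose in 7.1 and 12.5.1.

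Nor is it right that the trial holds no data below 17. Under 10.1.4.2, readings are taken at 80% to 20% of the matched dose during weaning; for a patient matched at 17 these are 13.6, 10.2, 6.8 and 3.4. Part II also titrates up from 3.4. But weaning readings come later, when need may have changed, Part II has no Veletri comparator, and no section uses either source for the equivalent dose.

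Finally, no document supports true medians of 10 to 14 specifically. The protocol's own estimate is 17, and there the effect is smaller.

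**Conclusion.** The point holds. The censoring at 17 follows from the dosing rules without any assumption, and so does the floor of 0.34 on the reported ratio. The size of the bias does depend on assumptions. With lognormal needs, CV 40%, n = 10 and steps of 3.4, the recorded mean exceeds the true mean by 6.7, 5.2, 4.1 and 3.0 ng/kg/min at true medians of 10, 12, 14 and 17. About 0.9 of the last figure is step rounding. At true medians above 20 the floor is a minor issue.

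The gap is shown for the protocol text only, since no SAP text is available. It should be fixed before database lock, but it does not undermine Part I: a conclusion that 17 is sufficient would remain valid where the data show it. It should not be presented as the necessary or equivalent dose.

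**What to change.** Leave dosing unchanged. In 12.5.1 and the SAP:

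1. Put each dosed Part I patient in one class: matched at 17 (17 or less); matched later (between the last failing and the first successful step); not matched because of conversion or extubation (above the last dose assessed as failing); or not assessable. Do not leave unmatched patients out.
2. Report the count in each class, with an exact 95% CI for the share matched at 17 among patients with a reading at that dose. For scale, 8 of 10 gives 44% to 97% and 9 of 10 gives 55% to 99.7%.
3. Report the median as a class or bound instead of a mean of recorded doses. With 6 or more of 10 matched at 17, it is 17 or less.
4. If the median falls in that class, conclude that 17 is sufficient, as an upper bound, and not that it is the necessary or equivalent dose.
5. Weaning readings may be shown as a sensitivity analysis only.

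Separately, section 2.1 judges similarity by a response at least equal to that on Veletri, while 4.1, 6.2.1, 6.3.3.1, 6.3.4.1 and 7.1 use 90% of it. These imply different stopping doses and must be reconciled.

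The cost is a paragraph in 12.5.1 and the SAP and one table. The downside is that the primary result may be an upper bound instead of a point value.
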